9.2. Patient safety and costs

The patient safety and cost data that will be used to address hypotheses H1a through H1e will be obtained from Medicare claims records. These records will be obtained through application to and purchase from the Research Data Assistance Center located at the University of Minnesota School of Public Health (ResDAC; <http://www.resdac.org/>). All requests for Medicare data proceed through ResDAC. We will obtain claims data from CMS for calendar years 2013 through 2016 and will construct three analysis cohorts, each including patients with a qualifying admission diagnosis: Baseline 1 (admission between 7/1/2013-6/30/2014), Baseline 2 (admission between 7/1/2014-6/30/2015), and Trial year (admission between 7/1/2015-6/30/2016). For each patient in each analysis cohort, we will obtain their encounters with the medical system for at least 6 months before and 6 months after the qualifying admission; hence the minimum age at qualifying admission is 65.5 years. Medicare data for the previous calendar year (Jan-Dec) are first made available by CMS to researchers each year around October. Data needed for creation of each analysis cohort of patients are shown per the table. We will request the following file types: MEDPAR (for inpatient encounters), Carrier for physician bills, Outpatient file (includes ED visits), Durable medical equipment, Hospice care, and Home care.

Analysis cohort (range of possible dates of qualifying admission)	Calendar year of CMS data of interest (earliest date available)
Baseline 1 (7/1/2013 - 6/30/2014)	2013 (Fall 2014) 2014 (Fall 2015)
Baseline 2 (7/1/2014 - 6/30/2015)	2014 (Fall 2015) 2015 (Fall 2016)
Trial year (7/1/2015 - 6/30/2016)	2015 (Fall 2016) 2016 (Fall 2017)

Use of 2 baseline periods provides for more stable estimates of the safety outcome measures and costs, especially for the low rate measures, such as 30-day mortality. Having more stable estimates helps with the power calculations to detect differences between **Flex** and **Curr**. The claims for Baseline 1 will be finalized in April 2016, allowing us to prepare analysis files, define and construct outcomes and develop risk adjustment models, such that when Baseline 2 claims are finalized in April 2017, we are able to apply the code we have developed for constructing and analyzing the data.

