11.2.2. Patient safety and costs

11.2.2.1.1. Patient safety hypothesis H1a - 30-day mortality

The primary outcome will be the difference in the pre-trial year and trial year mortality rates. The SD of the set of paired annual differences (2008 vs. 2007) in 30-day mortality from the preliminary data was equal to 1.5%. The mortality rates were similar across the two years: 11.1% and 11.5% for 2007 and 2008, respectively, consistent with minimal secular trends in mortality. The noninferiority sample size calculations described above show high power and low one-sided type-I error for the noninferiority hypothesis with a 1% margin.

The program level data needed for Specific Aim 1 outcome measures (patient safety and costs) will be aggregated into rates or other measures at the program level across two 1-year periods – the rates in the pre-trial year and the rates in the year of the trial. The outcome measure will be the change in these rates from the pre-trial year to the trial year and will be compared by treatment group using the same non-inferiority test proposed in the sample size justifications above.

The model (model A1) is:

$$Y_i = \gamma + \beta_1 x_i + \varepsilon_i, \quad i = 1, \dots, n_p \text{ where}$$

Y_i = Outcome measure in IM program i ,

γ = the intercept in the reference group (Curr),

β_1 = the difference in intercepts between Flex and Curr,

$x_i = 1$ if the i th IM program is in **Flex**, 0 if the i th IM program is in **Curr**

ε_i = i.i.d. random Gaussian errors with mean 0 and variance σ^2

n_p = Number of clusters (IM programs)

Tests of β_1 (or $\beta_1 - nim$, where nim is the noninferiority margin) estimated using linear regression will be used to test this hypothesis, since β_1 is the expected difference in outcome: **Flex** vs. **Curr**. All randomized programs will be included in this model and we expect no missing data.

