- Trainee education and process outcomes
 - Intern work intensity, ownership, and continuity measures (iCOMPARE surveys)
 - Intern time in direct patient care and other activities (Time and Motion Substudy)
 - Trainee satisfaction, burnout, and attitudes (iCOMPARE and ACGME surveys)
 - Intern knowledge (ACP ITE score)
 - Faculty satisfaction with training and teaching experience (ACGME survey)
 - Program director satisfaction and perceptions of training safety, teamwork and supervision (iCOMPARE and APDIM surveys)
- Intern sleep and alertness outcomes (Sleep and Alertness Substudy)
 - Sleep-wake times (wrist actigraphy)
 - Onset and offset times of sleep periods in past 24h (interview)
 - Perceived sleepiness (Karolinska Sleepiness Scale)
 - Behavioral alertness (psychomotor vigilance performance)

Sample size justification for mortality outcome

- Planned sample size: 58 graduate medical education training programs in Internal Medicine selected from ACGME list of candidate IM programs; the planned total number of hospitals across the training program clusters is 100+ (some programs span more than one hospital)
- Sample size determined to be adequate to test the hypothesis that 30-day mortality among Medicare beneficiaries in defined high risk DRGs (30-day mortality = 11%) in the intervention flexible schedule is not inferior to the corresponding mortality in the current 16 hour limit (control) schedule by a margin no greater than 1%
- Unit of analysis: IM training program
- Primary outcome measure: Difference (trial year vs. pre-trial year) in 1-year 30-day mortality
- Power: > 0.80
- Type I error (alpha): 0.05
- Primary analysis method: one-sided two-sample t-test for a noninferiority margin of 1%
- Software for sample size calculations: PASS 11

Recruitment goals

- 58 IM programs encompassing 100+ hospitals

Selection criteria for programs to be randomized

- Resident to bed ratio > 0.105 (excluded bottom 50% of hospitals by resident to bed ratio)
- Sufficient patient volume (excluded bottom 25% of hospitals by patient volume)
- Consent to participate
- Current ACGME accreditation

Consent issues

- ACGME has provided a waiver allowing programs to participate in COMPARE
- Programs: consent to randomization and obtain local IRB approval

- Hospitals: programs must provide evidence of buy in/consent of their hospitals
- Patients
 - They do not consent
 - They are not informed about the trial

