 - Their data (in files provided by Medicare) are identified for analysis on the basis of the hospital seen at, their diagnosis, their calendar time of treatment (and possibly other factors)
- Trainees
 - Do not consent to randomization
 - Do not consent to use of ACGME and ACP data – data will be provided aggregated at the program level
 - Do provide consent for participation in Time and Motion Substudy
 - Do provide consent for participation in Sleep and Alertness Substudy
 - Completion of iCOMPARE surveys will be described as voluntary and participation will reflect tacit consent
- Program directors and faculty
 - Faculty do not consent to randomization; program directors consent to randomization on behalf of their program and institution and program directors are required to provide documentation of institutional official approval
 - Do not consent to use of ACGME survey responses – Data will be provided aggregated at the program level
 - Completion of iCOMPARE surveys will be described as voluntary and participation will reflect tacit consent

Key dates

- Spring 2014 – initiate recruitment of IM programs
- Fall 2014 - randomize IM programs
- 1Jul2015 - interns in participating IM programs begin to follow the COMPARE assigned duty hour schedule
- Winter 2016 – receive 2013 and 2014 CMS claims (baseline years)
- 30Jun2016 - trial ends
- Oct2016 - receive 1st release of 2015 CMS claims
- Jan2017 - receive final release of 2015 CMS claims
- Oct2017 - receive 1st release of 2016 CMS claims
- Jan2018 - receive final release of 2016 CMS claims
- Mar2019 - Primary outcome paper/dissemination of results and implications
- Jun2019 - End of funding

[figure not shown]
Mode of support

- Grant from NHLBI
- Grant from ACGME

Research group members

- Participating IM programs, program directors and program coordinators
- Trainees in the participating IM programs
- Faculty at the participating IM programs
- CCC
- DCC
- Advisory Board

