Data collected directly from trainees and program directors through iCOMPARE surveys, actigraphy, and/or observation will be supplemented with data collected on trainees, program directors and faculty by national organizations such as the ACGME, the American College of Physicians (ACP) and the Association of Program Directors in Internal Medicine (APDIM). The time period of direct data collection by iCOMPARE survey, actigraphy, or observation will be May 2015 through June 2016. The data obtained from the ACGME, APDIM, and ACP includes responses to their 2015 and 2016 surveys (ACGME, APDIM) and ITE scores (ACP) from fall 2015 and fall 2016.

The Medicare claims data will be received, analyzed and stored at Children's Hospital of Philadelphia. Surveys are administered by the CCC located at University of Pennsylvania and responses are collected by the CCC; files will be transferred to the DCC periodically for review and analysis. Sleep and Alertness Substudy data will be collected by Pulsar, transferred to the Sleep and Alertness Substudy group for post collection processing, and then transferred periodically to the DCC for review and analysis. The data received by the DCC will be devoid of personal identifiers such as name, phone number, and email address. Time and Motion Substudy data will be collected by the Time and Motion Substudy group and transferred periodically to the DCC for review and analysis. The data received by the DCC will be devoid of personal identifiers such as name, phone number, and email address. Backup files of the database at the DCC will be generated and stored at regular intervals in a secure, off-site location, to permit regeneration of the database in the event that it is destroyed. Freeze dates for data sets created for interim and publication analyses will be documented.

3 Sample size and power

We approached the statistical design by designating the non-inferiority mortality hypothesis H1a (30-day patient mortality under **Flex** will not exceed (will not be inferior to) mortality under **Curr**) as the primary hypothesis for which sample size calculations were based. The 30-day mortality outcome measure is defined, for each IM program, as the difference between the 30-day mortality rate in the trial year minus the 30-day mortality rate in the pre-trial year. Section 4.1 includes details on the definition and analysis plan for the primary outcome.

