4.1 Patient safety hypothesis H1a – 30-day mortality

The primary outcome will be the difference between the pre-trial year and trial year 30-day mortality rates as described above.

The model (model A1) is:

$$Y_i = \gamma + \beta_1 x_i + \varepsilon_i, \quad i = 1, \dots, n_p \text{ where}$$

Y_i = Outcome measure in IM program i = Trial year rate - Pre-trial year rate,

γ = the intercept in the reference group (**Curr**),

β_1 = the difference in intercepts between **Flex** and **Curr**,

$x_i = 1$ if the i th IM program is in **Flex**, 0 if the i th IM program is in **Curr**

ε_i = i.i.d. random Gaussian errors with mean 0 and variance σ^2

n_p = Number of clusters (IM programs)

We will test β_1 (or $\beta_1 - nim$, where nim is the non-inferiority margin) ≤ 0 ; β_1 is the expected difference in outcome: **Flex** vs. **Curr**. All randomized programs will be included in this model and we expect no missing data.

The primary outcome measure for this cluster-randomized trial is the difference in 30-day mortality rates during the trial year versus the prior, which is 58 rate differences, 1 per randomized program, with a two-sample t-test for non-inferior patient mortality (difference no greater than 1%), comparing the **Flex** vs. **Curr** schedules. This approach permits the use of a simple model (two-sample non-inferiority t-test) for the set of at least $N=29$ pairs of trial year vs. pre-trial year differences in each group (**Curr** vs. **Flex**) in annual 30-day mortality rates following the paradigm elaborated by Hayes and Moulton (8) in their book on cluster randomized trials (CRTs). The model obviates the need for complex risk adjustment models, since it adjusts for secular trends in 30-day mortality that were common to all hospitals (e.g., severe flu season, technological improvements), as well as removing variation due to IM program population risk profiles (e.g., geography, patient characteristics) that are likely to cancel out by comparing successive years within IM program.

While these rate differences should adjust for most program to program differences in patient and institutional mix, we will also perform an important series of sensitivity analyses using risk-adjustment modeling methods that we developed (9) and which we will apply to the iCOMPARE data to confirm the findings of the primary analysis or to add a risk-adjustment caution to the statements of findings.

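### The primary mortality test subtracts one pre-trial year, although Protocol 9.2 obtains two baseline years to stabilise 30-day mortality and help power

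*Combined protocol and SAP*

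**What the plan says.** Protocol 9.2 defines Baseline 1 (admissions July 2013 to June 2014), Baseline 2 (July 2014 to June 2015) and the trial year. It says that two baselines give "more stable estimates of the safety outcome measures and costs, especially for the low rate measures, such as 30-day mortality", and continues: "Having more stable estimates helps with the power calculations to detect differences between" the two arms. It also gives Baseline 1 a preparatory use: building files, constructing outcomes and developing risk models before later claims arrive.

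Every definition of the primary outcome uses one pre-trial year:

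- SAP 3 and Protocol 11.1: "the difference between the 30-day mortality rate in the trial year minus the 30-day mortality rate in the pre-trial year".
- Protocol 11.2.2.1.1: data are "aggregated into rates or other measures at the program level across two 1-year periods", one pre-trial and one trial.
- Protocol 15.3: "Primary outcome measure: Difference (trial year vs. pre-trial year) in 1-year 30-day mortality".
- SAP 4.1: one rate difference per program, trial year against the year before, compared by a two-sample t-test. Model A1 contains an intercept, the arm indicator and error.

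The reason given in SAP 4.1 is that program risk profiles are "likely to cancel out by comparing successive years within IM program".

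**The concern.** The inconsistency lies within the Protocol. Section 9.2 names 30-day mortality and power as reasons for a second baseline, but section 11.2.2.1.1 leaves that year out without comment. The SAP follows 11.2.2.1.1.

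Two things are given up. Baseline 1 carries no weight in the primary test. In addition, subtracting Baseline 2 fixes its coefficient at 1, where a regression would estimate it. When a single year's rate is a noisy measure of a program's level, a coefficient of 1 over-corrects and adds variance.

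The primary test has one observation per program, 58 planned and 63 randomized, and power of 0.81 to 0.83. Randomization has closed, so precision can no longer be bought with more programs. A wider interval makes it more likely that the trial fails to exclude a 1-point excess in mortality when there is none.

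**Working it through.** **Inputs from the documents.** Margin 1 point, true difference 0, one-sided alpha 0.05, 29 programs per arm (SAP 3, Protocol 11.1). SD of the one-year change 1.5 points, from the single pair 2008 vs 2007 (Protocol 11.2.2.1.1). 63 programs randomized (Protocol 6.1), taken here as 31/32.

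**Step 1: the plan's own figure.** Standard error = 1.5 × √(2/29) = 0.394. Noncentrality = 1/0.394 = 2.54, with 56 degrees of freedom. The noncentral t gives power 0.8059, as stated; 40 per arm gives 0.9050, also as stated. With 31/32 the same test has power 0.834. The SD comes from one pair of single years, so these figures contain no gain from a second baseline.

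**Step 2: a model for three years (assumed).** A program's yearly rate is a stable level with between-program SD τ, plus yearly noise with variance s² and lag-one correlation r. Matching the documented SD requires 2s²(1 − r) = 1.5² = 2.25. The ranges are τ = 0.5 to 3 points and r = 0, 0.3, 0.5 and 0.7, plus a random walk as the worst case. The residual variance of the trial-year rate given the baselines is V − c′S⁻¹c. Here V is its variance, S the covariance matrix of the baseline rates, and c their covariances with the trial year.

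**Step 3: one case by hand (r = 0, τ = 2).** s² = 1.125, so V = 4 + 1.125 = 5.125, and any two years have covariance 4.

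- Baseline 2 only: slope 4/5.125 = 0.780. Residual variance 5.125 − 4 × 0.780 = 2.00, SD 1.415. Power (55 df) 0.844.
- Both baselines: each slope 4/(5.125 + 4) = 0.438. Residual variance 5.125 − 2 × 4 × 0.438 = 1.62, SD 1.272. Power (54 df) 0.905.

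**Step 4: chance imbalance.** With two covariates and 58 programs, the R² of arm on the covariates follows Beta(1, 27.5). The variance of the treatment estimate is multiplied by 1/(1 − R²), whose mean is 27.5/26.5 = 55/53. Power is averaged over that distribution.

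**Step 5: results at 29/29 over the range of τ.** The change score has power 0.806 throughout.

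| Yearly noise | Residual SD, both baselines | Power, balanced | Power, imbalance counted |
|---|---|---|---|
| Independent | 1.14–1.29 | 0.90–0.95 | 0.89–0.94 |
| AR(1), r = 0.3–0.7 | 1.25–1.46 | 0.825–0.914 | 0.81–0.90 |
| Random walk | 1.50 | 0.8056 | 0.793 |

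With imbalance counted, the regression beats the change score in all 20 stationary scenarios (0.813 to 0.944) and loses only under a random walk.

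**Step 6: a simple two-year average is not the answer.** Subtracting the mean of the two baselines gives SD 1.5 × √0.75 = 1.299 and power 0.894 with independent noise. Power falls to 0.772 at r = 0.7 and to 0.725 under a random walk.

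**Step 7: simulation, 20,000 trials per setting at 29/29.** Power of the regression against the change score:

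- independent noise, τ = 2: 0.892 vs 0.804
- r = 0.7, τ = 3: 0.815 vs 0.808
- random walk: 0.796 vs 0.808

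Type I error of the regression at a true difference of 1 point was 0.051 and 0.050.

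**The case against.** The current test contains no error. It is pre-specified consistently, gives a reason for using adjacent years, cites a cluster-trial text and meets the 80% target on documented inputs. Section 9.2 describes data collection and gives Baseline 1 a preparatory use. Regression adjustment is allowed if imbalance requires it (Protocol 8), and risk-adjusted models are planned (SAP 4.1.1 to 4.1.3). All of this is true, but none of it changes the primary test or explains why the stated stability and power purpose was not carried through. The adjacent-year rationale is kept when Baseline 2 remains its own covariate.

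The stronger objection is that much of the gain comes from estimating the Baseline 2 slope, not from adding Baseline 1. At τ = 1 and r = 0.5, the balanced-baseline power is 0.867 with Baseline 2 alone and 0.869 with both. With imbalance counted, adding Baseline 1 lowers power relative to Baseline 2 alone in 8 of the 15 AR(1) scenarios. This stands, but the loss is at most about 0.6 point, whereas Baseline 1 adds up to about 7 points when noise is independent.

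It is also fair that the gain depends on correlations the documents do not give, and that it is smaller where correlation is strong. With 63 programs and r = 0.7, the regression gives 0.842 to 0.870 against 0.834. Under a random walk it gives 0.823, and at 58 programs 0.793, which is below the 80% target.

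**Conclusion.** The concern holds, as a matter of efficiency and internal consistency. Validity is not in question. At 58 programs the change in power runs from a loss of about 1.3 points (random walk) to a gain of about 14 points (independent noise, small between-program SD). For scale, the plan's own table needs 22 more programs, 58 to 80, to reach 0.905. Where in that range the trial lies depends on the assumed between-program SD and between-year correlation, so confidence in the size is medium. The mismatch between Protocol 9.2 and 11.2.2.1.1 needs correcting whatever the size. The change is worth making because the possible gain is large against a small, known downside.

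**What to change.** Before trial-year data are seen, make the primary model:

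trial-year 30-day mortality = intercept + b1 × Flex + b2 × Baseline 2 rate + b3 × Baseline 1 rate + error.

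- Test b1 against the same 1-point margin at the same one-sided alpha.
- Keep the single-year change-score t-test as a sensitivity analysis.
- Conform the outcome definitions in Protocol 11.1, 11.2.2.1.1 and 15.3 and SAP 3 and 4.1, and Model B in SAP 4.1.1.
- Use the same approach for H1b to H1d where they are analysed as program-level rates with the linear model.
- If the one-year change score is kept, say in Protocol 9.2 and 11.2.2.1.1 that Baseline 1 is not in the primary test, and why.

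**Cost.** Two degrees of freedom (0.8059 to 0.8056 at an unchanged SD), the worst-case power loss given above, and edits to five definitions and Model B in a plan that the DSMB has approved. No new data are needed, since claims for both baseline years are already planned. There is time: the SAP is dated 22 December 2015, and Protocol 15.3 lists "Jan2018 - receive final release of 2016 CMS claims".

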Hypothesis H3a was designated as the primary hypothesis for the Sleep and Alertness Substudy. For H3a, with 90% power, one-sided Type I error of 0.05, and a non-inferiority margin of 0.5 hours, the required sample size is 290 interns. The proposed sample size is higher: 384 interns (48 at each of 8 programs) for H3a.

4 Data analysis

4.1 Patient safety hypothesis H1a – 30-day mortality

The primary outcome will be the difference between the pre-trial year and trial year 30-day mortality rates as described above.

The model (model A1) is:

$$Y_i = \gamma + \beta_1 x_i + \varepsilon_i, \quad i = 1, \dots, n_p \text{ where}$$

Y_i = Outcome measure in IM program i = Trial year rate - Pre-trial year rate,

γ = the intercept in the reference group (**Curr**),

β_1 = the difference in intercepts between **Flex** and **Curr**,

$x_i = 1$ if the i th IM program is in **Flex**, 0 if the i th IM program is in **Curr**

ε_i = i.i.d. random Gaussian errors with mean 0 and variance σ^2

n_p = Number of clusters (IM programs)

We will test β_1 (or $\beta_1 - nim$, where nim is the non-inferiority margin) ≤ 0 ; β_1 is the expected difference in outcome: **Flex** vs. **Curr**. All randomized programs will be included in this model and we expect no missing data.

The primary outcome measure for this cluster-randomized trial is the difference in 30-day mortality rates during the trial year versus the prior, which is 58 rate differences, 1 per randomized program, with a two-sample t-test for non-inferior patient mortality (difference no greater than 1%), comparing the **Flex** vs. **Curr** schedules. This approach permits the use of a simple model (two-sample non-inferiority t-test) for the set of at least $N=29$ pairs of trial year vs. pre-trial year differences in each group (**Curr** vs. **Flex**) in annual 30-day mortality rates following the paradigm elaborated by Hayes and Moulton (8) in their book on cluster randomized trials (CRTs). The model obviates the need for complex risk adjustment models, since it adjusts for secular trends in 30-day mortality that were common to all hospitals (e.g., severe flu season, technological improvements), as well as removing variation due to IM program population risk profiles (e.g., geography, patient characteristics) that are likely to cancel out by comparing successive years within IM program.

While these rate differences should adjust for most program to program differences in patient and institutional mix, we will also perform an important series of sensitivity analyses using risk-adjustment modeling methods that we developed (9) and which we will apply to the iCOMPARE data to confirm the findings of the primary analysis or to add a risk-adjustment caution to the statements of findings.

